6.5.2 Secondary Efficacy Endpoints

Key Secondary Efficacy Endpoints

The key secondary efficacy endpoints are change in VAS for pain and change in FACIT fatigue scale. In order to control the rate of false positive conclusions, the serial gatekeeping methodology (fixed-sequence test) will be employed to control for multiple (primary and key secondary) endpoints in this order.

Change in VAS score for Pain

The VAS is a subjective measure of pain and it consists of a 100 mm line with two endpoints representing “no pain” and “pain as bad as it could be”. Patients are asked to rate their pain by placing a mark on the line corresponding to their current level of pain. The distance along the line from the ‘no pain’ marker is then measured with a ruler giving a pain score out of 10.

The change in VAS for pain score from baseline to Week 24 in the double-blind period will be analyzed by analysis of covariance (ANCOVA) method with baseline observation carried forward (BOCF) imputation. The analysis will include the categorical effects for treatment, prior therapy for prevention of NMO/NMOSD attack and the most recent attack in the last one year prior to screening, as well as the continuous covariates of baseline VAS for pain score.

Change in FACIT Fatigue Score

FACIT fatigue scale includes 13 questions, which measure fatigue/asthenia for patients with chronic, life-threatening illnesses. For each question, a patient rates his / her condition for the past week on a 5-point Likert scale ranging from 0 (not at all) to 4 (very much). For the change in FACIT fatigue, descriptive statistics will be calculated for the change in FACIT fatigue by averaging the individual question scores.

The change in FACIT fatigue Scale score from baseline to Week 24 in the double-blind period will be analyzed by ANCOVA method with BOCF imputation. The analysis will include the categorical effects for treatment, prior therapy for prevention of NMO/NMOSD attack and the most recent attack in the last one year prior to screening, as well as the continuous covariates of baseline FACIT fatigue score.

Further Secondary Efficacy Endpoints

Change in Short Form Generic Health Survey (SF-36) Score

The scores will be presented and summarized for each of the 8 domains (vitality, physical functioning, bodily pain, general health, role-physical, role-emotional, social role functioning and mental health) and 2 summary components (physical and mental). The mean change in SF-36 domain scores will be analyzed from baseline to every 24 weeks after the baseline visit.

Change in EQ-5D Score

The EQ-5D is a participant-answered questionnaire measuring 5 dimensions of mobility, self-care, usual activities, pain/discomfort, and anxiety/depression with 3 possible response categories: 1) no problems; 2) some problems; 3) severe problems. The EQ-5D is therefore able to represent 243 (3^5) distinct health states. These states may then be converted into a single index value by using the time trade-off based tariff methods. The best possible answer would be (1,1,1,1,1) and the worst possible answer would be (3,3,3,3,3). A shift table will be used to evaluate the number and percentage of patients having a different post-baseline status when compared to their baseline status. The mean change in EQ-5D score will be analyzed from baseline to every 24 weeks after the baseline visit.

Change in Timed 25-Foot Walk (T25W)

The T25W is the measurement to assess the walking ability. The time (in seconds) that it takes the patient to walk 25 feet is measured. The mean change of the amount of time will be analyzed from baseline to every 24 weeks after the baseline visit.

The Proportion of Relapse-free Patients

The proportion of patients who are relapse-free during *the* double-blinded period and *the* entire study (*double-blind and OLE periods combined*) will be calculated for the two treatment groups. *When both periods are analyzed together, patients are analyzed as randomized, even if patients randomized to placebo receive satralizumab in the OLE period.*

The Kaplan-Meier estimates and corresponding 95% CIs for the proportion of patients who were relapse-free during the double-blind period are calculated for both treatment groups.

Relapse-free rates will be analyzed at every 24 weeks after baseline.

Annualized Relapse Rate (ARR)

The relapse episodes for each eligible patient will be recorded throughout the whole study. The ARR is calculated as the total number of relapses experienced divided by the

person-years at risk for each year of the study period. The 95% CI will be presented based on the Poisson distribution.

For comparing the difference between two treatment arms, negative binomial regression model will be used with ARR as response variable; treatment group, prior therapy for prevention of NMO/NMOSD attack (B-cell depleting therapy or immunosuppressants/others), and the *type of the* most recent attack in the last one year prior to screening (first attack or relapse) as covariates.

Change in Modified Rankin Scale Score

The mRS is a 7-point disability scale that assesses the degree of disability in patients with neurological impairment. Possible scores range from 0 (no symptom at all) up to 6 (death). The higher scores reflect increased disability. Descriptive statistics will be calculated for the change in mRS.

The mean change in mRS score will be analyzed from baseline to every 24 weeks after the baseline visit.

Change in Zarit Burden Interview Score

The ZBI is the measurement to assess caregiver burden. The 22 items ask for the strain caregivers perceive. Responses range from 0 (never) to 4 (nearly always) with maximum score of 88. The higher the total score, the heavier the perceived burden. Descriptive statistics will be calculated for the change in ZBI.

The mean change in ZBI score will be analyzed from baseline to every 24 weeks after the baseline visit.

Change in Expanded Disability Status Scale (EDSS) Score

The EDSS will be assessed on scheduled visits during entire study. The mean change in EDSS scores from baseline to every 24 weeks after the baseline visit will be analyzed.

Time to EDSS worsening based on the definition for PDR is estimated with a cox regression with treatment group, prior therapy for prevention of NMO/NMOSD attack (B-cell depleting therapy or immunosuppressants/others), and the type of the most recent attack in the last year prior to screening (first attack or relapse) as covariates. The hazard ratio and 95% CI for the treatment groups is estimated in this model, the p-value is calculated based on the log rank test. In addition, Kaplan-Meier estimate of event-free rates will be provided.

These analyses are done for the double-blind period and the combined double-blind and OLE period. When both periods are analyzed together, patients are analyzed as

randomized, even if patients randomized to placebo receive satralizumab in the OLE period.

Change in Visual Acuity (Snellen Chart)

Visual acuity will be measured by a Snellen 20-foot wall chart. The test will be performed monocularly and patients may use their habitual distance glasses or contact lenses.

The same visual acuity testing method is to be employed for all study visits for each patient.

Change in low-contrast visual acuity (Low-contrast Sloan letter chart (LCSLC))

The LCSLC is the testing to evaluate the visual function and captures the minimum size at which individuals can perceive letters of a particular contrast level. The change in binocular visual acuity, as assessed by the number of letters read correctly from 2 meters distance on 100% (high contrast, used to measure visual acuity as a descriptor of the study cohorts), 2.5% and 1.25% contrast level Sloan letter charts, will be analyzed from baseline to every 24 weeks after the baseline visit.

A mixed-effects model repeated measures (MMRM) analysis will be used for the change from baseline in EDSS, SF-36, VAS for pain, FACIT fatigue, T25W, mRS, ZBI and EQ-5D scores, as well as visual function testing (including visual acuity tests of Snellen and low-contrast Sloan letter chart). The model will include treatment group, protocol-specified visit, treatment-by-visit interaction as fixed effects; the baseline measurements as a covariate; and visit as a repeated measure. *An* unstructured covariance matrix will be assumed in the model.

If the unstructured covariance matrix does not converge, other covariance structure will be used. If treatment-by-visit interaction is not statistically significant, we still keep the full model.

If the normality assumption for the secondary efficacy variable does not hold, a generalized estimating equation or Generalized Linear Mixed-effect model analysis will be used. The assessment will be performed prior to un-blinding and details will be mentioned in the SAP.

Use of rescue medication

The use of rescue medication is based on treated clinical relapses. If a patient has at least one treated clinical relapse, then this patient is counted as a patient with rescue medication use. The use of rescue medication will be analyzed with a logistic regression model with treatment group, prior therapy for prevention of NMO/NMOSD attack (B-cell depleting therapy or immunosuppressants/others), and the type of the

most recent attack in the last year prior to screening (first attack or relapse) as covariates. The odds ratio, corresponding 95% CI, and p-value for the treatment group will be reported. This analysis is conducted for the double-blind period.

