4.1.1 Inclusion Criteria

Patients must meet the following criteria for study entry:

1. Patients must be diagnosed as either:
 - a. NMO as defined by Wingerchuk 2006 criteria*, or
 - b. NMOSD as defined by either of *the* following criteria with anti-AQP4 antibody seropositive status at screening.
 - i. Idiopathic single or recurrent events of longitudinally extensive myelitis (≥ 3 vertebral segment spinal cord MRI lesion)
 - ii. Optic neuritis, single, recurrent or simultaneous bilateral
2. Clinical evidence of at least 1 documented relapse (including first attack) in the last 12 months prior to screening.
3. EDSS score from 0 to 6.5 inclusive at screening.
4. Age 18 to 74 years, inclusive at the time of informed consent.
5. Ability and willingness to provide written informed consent and to comply with the requirements of the protocol.

*According to Wingerchuk et al. 2006, a diagnosis of NMO requires all of following criteria:

- I. Optic neuritis
- II. Acute myelitis
- III. At least two of three supportive criteria:
 - Contiguous spinal cord lesion identified on an MRI scan extending over 3 vertebral segments
 - Brain MRI not meeting diagnostic criteria for multiple sclerosis

- NMO-IgG seropositive status

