4.5 STUDY ASSESSMENTS

4.5.1 Description of Study Assessments

4.5.1.1 Medical History and Demographic Data

Medical history refers to clinically significant diseases, including but is not limited to medication allergies, anaphylaxis, cancer, demyelinating disease other than NMO and NMOSD, neurologic disorders, psychiatric disorders, rheumatologic disorders, musculoskeletal diseases, cardiovascular disease, pulmonary disease, gastrointestinal diseases including hepatic diseases, hematologic disorders and renal disease.

Demographic data will include age (date of birth), sex and race/ethnicity. These data are required in order to perform subgroup analyses to evaluate the consistency of the results across race/ethnic groups. Previous relapse (including first attack) *and date of NMO or NMOSD diagnosis* will be recorded in the eCRF. Height will be recorded at baseline and body weight will be recorded at baseline and every 24 weeks thereafter.

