6.2 DETERMINATION OF SAMPLE SIZE

Approximately 90 patients need to be recruited and randomized in a 2:1 ratio to the two treatment groups (satralizumab and placebo). The sample size considerations are based on the following assumptions:

- A two-sided log-rank test.
- At least 80% power at the 5% significance level.
- The hazard ratio of satralizumab over placebo for an initial 2 months from randomization is 1.0. The hazard ratio after an initial 2 months from randomization is 0.25.
- TFR in the placebo arm following an exponential distribution, with hazard rate for 1 year $h(t) = 1.1295$.
- A 2-year dropout rate of 10%.

Based on the assumptions, 44 TFR events are needed for the primary analysis. The 90 patients enrolled over 33 months and followed for an additional 5 months will provide 44 TFR events. The primary analysis will be performed once 44 TFR events have been observed or 1.5 years after the date of randomization of the last patient enrolled, whichever comes first. The Sponsor will conduct a blind review of the data including accumulation of events during the double-blind period and may take appropriate action such as to increase the number of patients or to extend the double-blind period based on this blind review.

It has been assumed that the number of relapses will follow a Gamma-Poisson distribution and that the variance/mean ratio will be a constant value of $\sqrt{2}$. This distribution was assumed and the ratio was estimated using data from MS trials (Gold et al. 2012; Kappos et al. 2010) because there are no approved medications for NMO and no raw data from patients with this indication are available.

Because the mean ARR of NMO patients is estimated at 0.82 and eligibility criterion 2 says patients at least 1 relapse in last 12 months prior to screening are selected, we calculate the zero-truncated mean of the Gamma-Poisson distribution with the mean of 0.82 and the mean and variance ratio of $\sqrt{2}$, then the baseline ARR is estimated at 1.65. The post-treatment ARR in the placebo group in NMO patients with anti-AQP4 positive and negative is estimated as 1.5 and 1.0, respectively (Cree et al. 2015). Given that the proportion of patients who are negative for anti-AQP4 antibody at screening will be capped at 30% of the total number of patients in this study, post-treatment ARR is estimated as 1.35.

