6.4 SUMMARY OF TREATMENT GROUP COMPARABILITY

Demographics (age, sex, race/ethnicity and concomitant medication) and baseline characteristics (hepatitis status, baseline annual relapse rate and number of previous episodes within one year before enrollment) of patients will be collected at screening or baseline visit before administration of first dose of study treatment.

In general, data will be summarized by treatment group and for all patients in the study (i.e., independent of treatment group). Descriptive statistics will be presented for continuous data with sample size, mean, standard deviation (SD), median, minimum, and maximum. Frequency table with percentage will be presented for discrete data.

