4.10.3.2 Other Secondary Endpoints

The following summary tables, figures and analysis will be provided for the ITT:

- A summary table of change in SF-36 domain scores from baseline to every 24 weeks.
- A summary table of change in SF-36 summary score (physical and mental) from baseline to every 24 weeks.
- A summary table of change in EQ-5D scores from baseline to every 24 weeks.
- A summary table of change in T25W from baseline to every 24 weeks.
- A summary table of the proportion of relapse-free patients.
- A summary table of ARR.

The ARR is calculated as the total number of relapses experienced divided by the person-years at risk. The 95% CI will be presented based on the Poisson distribution. ARR based on the person-years at risk on the total study period will also be provided. In order to account for different study treatment exposure durations among subjects, log-transformed exposure time will be included in the model as an "offset" variable for appropriate computation of ARR.

- A summary table of ARR for patients with clinical relapse.
- A summary table of ARR for patients with treated clinical relapse.
- Analysis of ARR will be performed using negative binomial regression model (protocol-defined relapse).

For comparing the difference between 2 treatment arms, relapse number will be the response variable; treatment group, prior therapy for prevention of NMO/NMOSD attack (B-cell depleting therapy or immunosuppressants/others) and the most recent attack in the last one year prior to baseline (first attack or relapse) as covariates. Logtransformed exposure time will be included in the model as an "offset" variable.

A summary table of change in mRS scores from baseline to every 24 weeks.

TP-GDO-WW-016-01 Confidential Version 7.0 Effective Date: 28Aug13 Version Date: 28NOV2018 Related to: SOP-GDO-WW-019

- A summary table of change in ZBI scores from baseline to every 24 weeks.
- A summary table of change in EDSS scores from baseline to every 24 weeks.
- A summary table of change in visual acuity (Snellen chart) scores from baseline to every 24 weeks.
- A summary table of change in low-contrast visual acuity (Low-contrast Sloan letter chart [LCSLC]) scores from baseline to every 24 weeks.
- Analysis of change in SF-36 domain scores from baseline to every 24 weeks using MMRM analysis.
- Analysis of change in SF-36 components (physical and mental) from baseline to every 24 weeks using MMRM analysis.

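### The relapse-rate model leaves out the prior-year relapse count, which is the natural baseline for ARR and is already recorded; adding it gives a small gain at almost no cost

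*Protocol*

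**What the plan says.** Protocol 6.5.2 compares the arms on ARR with a negative binomial regression: "negative binomial regression model will be used with ARR as response variable; treatment group, prior therapy for prevention of NMO/NMOSD attack", followed by type of most recent attack. SAP 4.10.3.2 fits the model to a count with a log-exposure offset: "relapse number will be the response variable; treatment group, prior therapy for prevention of NMO/NMOSD attack", again followed by type of most recent attack. The SAP specifies this regression for protocol-defined relapses only. ARR for clinical and treated clinical relapses gets summary tables.

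Relapse history is collected. Protocol 4.5.1.1 sends previous relapses, first attack included, to the eCRF. Protocol 6.4 lists "baseline annual relapse rate and number of previous episodes within one year before enrollment" among the baseline characteristics, although the list in SAP 4.6 does not repeat it. Inclusion criterion 2 requires "Clinical evidence of at least 1 documented relapse (including first attack) in the last 12 months prior to screening".

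The other secondary models do use their own baseline: the ANCOVAs for VAS pain and FACIT fatigue and all the MMRM analyses (Protocol 6.5.2, SAP 4.10.3.1 and 4.10.3.2).

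**The concern.** In relapsing disease the obvious baseline counterpart of the on-study relapse rate is the relapse count over the preceding year. The plan applies baseline adjustment to every continuous secondary endpoint but not to ARR. The design also assumes that "the number of relapses will follow a Gamma-Poisson distribution", which means patients with different underlying rates. If those differences are stable within patients, leaving the count out puts explainable variation into the dispersion term and widens the interval for the rate ratio. A chance imbalance in relapse history between about 30 placebo and 60 satralizumab patients would also be corrected only as far as attack type captures it. What is at stake is the precision of one further secondary endpoint, not the validity of the comparison.

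**Working it through.** **1. Reproduce the plan's relapse model** (Protocol 6.2, SAP 4.14: mean 0.82, variance/mean V = √2). For a Gamma-Poisson count with mean m, P(0) = V^(−m/(V−1)).
- P(0 | 0.82) = 0.5035, so the zero-truncated mean is 0.82/(1 − 0.5035) = 1.65, as stated.
- P(0 | 1.35) = 32.3% and −ln 0.323 = 1.1295, both as stated.

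**2. What the count would tell us if rates persist.** Gamma shape k = 0.82/0.4142 = 1.98, scale θ = 0.4142, θ/(1+θ) = 0.2929. The expected rate after x prior-year relapses is (k + x) × 0.2929: 0.87, 1.17 and 1.46 per year for x = 1, 2, 3. The mean among eligible patients is (1.98 + 1.65) × 0.2929 = 1.06. Scaling by 1.35/1.06 to the plan's placebo rate gives about 1.1, 1.5 and 1.85. About 59% of eligible patients have a count of exactly 1, and the simulated correlation of the count with the next year's count is only 0.24.

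**3. Effect on the ARR comparison.** Simulated trials of 90 patients (2:1) were analysed with the SAP's model with and without log(count). Treatment, prior therapy and attack type were in both models. Assumptions not in the documents: full persistence of each patient's rate (except the last row), 20% with prior B-cell therapy where this was set, and the share of count-1 patients whose attack was their first (shown as FA). The plan's effect means a ratio of 1.0 for 2 months, then 0.25. Rate ratios (RR) of 0.5 and 0.6 are assumed. Runs per row: 4,000 (rows 1–3), 1,500 (rows 4–6), 3,000 (rows 7–9).

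| Setting | SE of log rate ratio | Change | Power |
|---|---|---|---|
| First relapse only, plan's effect, FA 0% | 0.378 → 0.374 | −1.1% | 61.3 → 63.5% |
| First relapse only, plan's effect, FA 50% | 0.379 → 0.376 | −0.9% | 60.9 → 62.9% |
| All relapses, 1 year, plan's effect, FA 50% | 0.274 → 0.270 | −1.3% | 94.1 → 94.6% |
| All relapses, 1 year, RR 0.6, FA 30% | 0.249 → 0.244 | −2.0% | 54.5 → 55.7% |
| All relapses, 5–38 months, RR 0.6, FA 30–50% | 0.208 → 0.201 | −3.4% | 69 → 71% |
| All relapses, 5–38 months, RR 0.5, FA 30% | 0.214 → 0.206 | −3.7% | 89 → 90.5% |
| V = 2 (assumed), first relapse only, FA 50% | 0.394 → 0.381 | −3.4% | 58.7 → 63.7% |
| V = 2 (assumed), all relapses, 1 year, FA 50% | 0.293 → 0.280 | −4.6% | 90.5 → 92.9% |
| No persistence, first relapse only, FA 50% | 0.381 → 0.383 | +0.6% | 61.9 → 62.2% |

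In the first two rows variance falls about 2%. The squared mean z statistic rises about 5%, partly because the estimate itself moves slightly (for example −0.850 to −0.865). At a constant hazard ratio of 0.5 with first relapse only (800 runs), the SE hardly moves (0.338 in both models) and power goes from 56.9% to 58.4%. In the no-persistence row variance rises 1.15%.

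Under no treatment effect (all relapses, FA 30%), rejection is 6.3% without the covariate and 6.1% with it, so adding it does not inflate the error rate.

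**The case against.** The case against is that this is a modelling preference with little to gain, and much of it stands.

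- **The analysis actually run is the one that gains least.** The SAP's regression counts protocol-defined relapses, SAP 4.10.3 places efficacy analyses in the double-blind period, and Protocol 4.3.2.1 ends that period at the patient's first adjudicated relapse. In effect there is at most one event per patient. ARR over the total study period is also to be given, but by then placebo patients may be on open-label satralizumab, so a constant randomised rate ratio over 5 to 38 months does not describe it either.
- **Part of the information is already in the model.** Attack type is a stratum and a covariate, and a patient whose most recent attack was the first has a count of 1.
- **Persistence is not documented and may be weak.** Prior-year relapses may have occurred on drugs that Protocol 4.4.2 prohibits during the double-blind period. A first-attack patient's count does not reflect a full year at risk of relapse.
- **log(count) can be undefined.** ITT is all randomised patients, and Protocol 6.3 foresees eligibility deviations. A patient randomised with no prior-year relapse would drop out of the model. This objection shapes the fix.

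Two stronger readings are tempting. A reader might take the contrast between a mean ARR of 0.82 and a placebo rate of 1.35 as proof that relapse history predicts later relapses. It is not: 1.35 is 0.7 × 1.5 + 0.3 × 1.0, a weighting by AQP4 status of estimates from another cited source. A reader might also infer a gain of about four power points (66% to 70%) by simulating all relapses over 5 to 38 months at a rate ratio of 0.6. The documents do not specify a double-blind regression of that kind, and with attack type in both models the gain in that setting is about 2 points.

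**Conclusion.** The point holds as a minor efficiency improvement. The prior-year count is absent from the ARR model in both documents, it is recorded, and it is the natural baseline value for this endpoint. Leaving it out does not bias the randomised comparison. It does not touch alpha control, because the fixed sequence runs from time to first relapse to VAS pain to FACIT fatigue (SAP 4.10.1.4).

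The size rests on the plan's own heterogeneity (V = √2) and on the undocumented assumption that rates persist. On that basis the gain is about 0 to 2 power points for double-blind protocol-defined relapses, and a 3 to 4% smaller SE if all relapses over longer follow-up were analysed under a constant rate ratio. Stronger heterogeneity than the plan assumes would raise the gain. Without persistence there is none, and variance rises about 1%.

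**What to change.** In SAP 4.10.3.2, with matching wording in Protocol 6.5.2, pre-specify log(max(number of relapses in the 12 months before screening, 1)) as an added covariate in the negative binomial ARR model. Keep prior-therapy class, attack type and the exposure offset. Taking the maximum with 1 keeps any patient randomised in breach of inclusion criterion 2 in the ITT analysis. The primary stratified log-rank test is unchanged. Listing the count by arm in SAP 4.6, as Protocol 6.4 already intends, would also show any imbalance.

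This should be fixed before unblinding. Protocol Version 10 post-dates the completed double-blind period and refers to its results (Protocol 1.3, 5.1.1.6). If the data are already unblinded, keep the planned model as the main ARR analysis and report the extended model as a labelled sensitivity analysis.

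The cost is one sentence of wording and one parameter, using data already on the eCRF, with about 1% more variance if the count proves uninformative.
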